## **5.16.1. Data Handling**

### **5.16.1.1. Pharmacokinetic Profile Exclusions**

Changes to the procedures or events which may impact the quality of the PK data, will be considered important protocol deviations or events and will be described within the clinical study report body text. These events will include any circumstances that will alter the evaluation of the PK. Examples include, but may not be limited to, vomiting following oral dosing occurring within the time frame of 2 times the median  $T_{max}$ , sample processing errors that lead to inaccurate bioanalytical results, and/or inaccurate dosing on the day of PK. In the case of an important event, PK data collected during the affected treatment day will be evaluated on a case-by-case basis, be listed but may be excluded from descriptive statistics. Other changes to the procedures or events which do not impact the quality of the PK data will not be considered important events. All exclusions will be documented throughout the affected data listings.

### **5.16.1.2. Data Rounding**

Data rounding specifications for PK data are documented in the PK Table, Listing, and Figure (TLF) shells. Pharmacokinetic parameters will be rounded for reporting purposes both in the summary tables and individual listings. The unrounded derived PK data will be considered the source data for the calculation of descriptive statistics and the statistical analysis. All concentration data will be reported and analyzed with the same precision as the source data regardless of how many significant figures or decimals the data carry. For most derived PK parameters, 3 significant digits will be used as the standard rounding procedure, with the following exceptions:

- Parameters directly derived from source data (e.g.,  $C_{max}$ ) will be reported and analyzed with the same precision as the source data.
- Parameters derived from actual elapsed sample collection times (e.g.,  $T_{max}$ ) will be reported in hours with 2 decimal places.

For the reporting of descriptive statistics for concentrations and PK parameters, the mean (arithmetic or geometric) and SD will be presented to 1 digit more precision than the source data. The minimum, median, and maximum will be presented to the same precision as the source data.

Coefficient of variation and GeoMean CV% will be reported to 1 decimal place. Percentage will be reported using 1 decimal place, if not otherwise specified. N and n will be presented to 0 decimal place.

#### **5.16.1.3. Below the Limit of Quantification Values**

Plasma concentrations that are below the limit of quantification (BLQ) will be reported as the source data on the data listings. Plasma concentrations that are BLQ will be treated as zero for calculation of concentration descriptive statistics. Mean concentrations will be reported as zero if all values are BLQ, and no other descriptive statistics will be reported. If the calculated mean concentration is below the limit of quantitation, the mean will be reported as BLQ and the SD and CV% shall be reported as not determined (ND). Minimum, median, and maximum may be reported and, if any are BLQ, they shall be reported as such and indicated as BLQ.

For PK analysis, all BLQ values will be treated as zero, with the exception of BLQ values observed between 2 quantifiable concentrations which will be set to missing. Missing values will not be imputed. Additionally, if consecutive BLQ concentrations are followed by quantifiable concentrations in the terminal portion of the plasma concentration-time curve, these quantified values will be excluded from the PK analysis by setting them to missing, unless otherwise warranted by the concentration-time profile.

#### **5.16.1.4. Missing Data**

All missing concentration data will be presented as missing in concentration data listings and excluded from the concentration summary statistics. However, for the estimation of PK parameters for Day 24, missing predose concentrations will be imputed as the end of dosing interval (tau) concentration, where measurable. This imputation will be performed programmatically in the PK analysis input file.

Otherwise, missing results will be treated as missing and not imputed.

#### **5.16.1.5. Predose Samples Collected Postdose**

Predose samples collected in error after dosing will be listed, flagged and excluded from the calculation of concentration summary statistics; however, will be included in the estimation of PK parameters using the actual time relative to dosing.

#### **5.16.1.6. Summary Statistics**

Quantitative variables will be summarized using descriptive statistics as follows:

- Plasma concentrations: number of subjects, number of non-missing observations, arithmetic mean, standard deviation, percent coefficient of variation, median, minimum, and maximum.
- Plasma PK parameters: N, n, arithmetic mean, SD, CV%, geometric mean, geometric mean CV%, median, minimum, and maximum.  $T_{max}$  will be summarized using N, n, median, minimum, and maximum only.

A minimum of n=3 is required for all descriptive statistics to be generated. If n is less than 3, only N, n, minimum, and maximum will be reported.

### 5.16.2. Pharmacokinetic Analysis

Plasma concentration-time data will be analyzed by non-compartmental methods using Phoenix® WinNonlin® Version 8.3 or higher (Certara USA, Inc., Princeton, NJ) or SAS® (SAS Institute Inc., Cary, North Carolina) Version 9.4 or higher. The following PK parameters will be calculated on Day 24 for CVL-231 (emraclidine) and its metabolite (CV-0000364), where data permit:

PK Parameter	Definition
C max	Maximum (peak) observed concentration.
T max	Time of maximum (peak) observed concentration.
AUC 0-last	AUC from time 0 to the last measurable concentration (C last ), calculated using the linear up log down trapezoidal rule.
AUC 0-tau	Area under the plasma concentration time curve over the dosing interval, calculated using the linear up log down trapezoidal rule.

AUC0-tau will not be calculated if  $\lambda_z$  cannot be determined or is not reliable to extrapolate to tau.

Additional PK parameters may be calculated.

Actual sampling times will be used for the estimation of all plasma PK parameters, and all concentrations associated with scheduled sampling times will be included in the analysis (including concentrations collected outside predefined collection windows). Unscheduled PK samples will not be included in the estimation of PK parameters.

Plasma PK parameters for CVL-231 (emraclidine) and metabolite CV-0000364 will be presented in data listings and summarized using descriptive statistics (see [Section 5.16.1.6](#)) by analyte and treatment. Any excluded parameters will be flagged and included in the individual listings.

### 5.17. Protocol Deviations

All protocol deviations will be reviewed by the project team prior to unblinding to identify subjects with important protocol deviations. Summaries of important deviations will be presented by category of deviation. All deviations from the protocol will be listed by category along with a description and any additional comments.

## 6. CHANGES IN THE PLANNED ANALYSES

Should any deviations from the analyses specified in the authorized statistical analysis plan arise, such deviations will be documented in the final clinical study report.

## 7. REVISION HISTORY

Date	Revision	Rationale

**9. APPENDICES**

## 9.1. Schedule of Assessments

**Table 4: Schedule of Assessments**

Trial Periods/Phases	Screening Period a,b,c	Treatment Period										Follow-up d
		-2 to -1	-	1	2	3 e	-	4	5	6 f	ET g	
Week	-2 to -1	-	-	1	2	3 e	-	4	5	6 f	ET g	10
Day	-15 to -1	1/ Baseline h	4	7±2	14±2	21±2	24	28±2	35±2	42±2	45±2	NA
Entrance and History												
Informed consent	X											
Inclusion/exclusion criteria	X	X i										
Medical and psychiatric history j	←-----→											
MINI	X											
Demography	X											
History of drug and alcohol use	X											
Smoking history	X	X										
Review of birth control methods	X											
Breathalyzer test for alcohol k	X											
SARS-CoV-2 testing c	X											
Randomization		X										
Efficacy/Health Economics Assessmentsl												
PANSS	X	X		X	X	X		X	X	X		X
CGI-S	X	X		X	X	X		X	X	X		X
CGI-I m						X				X		X

Trial Periods/Phases	Screening Period a,b,c	Treatment Period										Follow-up d
		-	-	1	2	3 e	-	4	5	6 f	ET g	
Week	-2 to -1	-	-	1	2	3 e	-	4	5	6 f	ET g	10
Day	-15 to -1	1/ Baseline h	4	7±2	14±2	21±2	24	28±2	35±2	42±2	45±2	NA
BACS		X								X	X	
SF-6D		X								X	X	
Safety Assessments												
Physical/neurological examination n	X									X	X	
Limited physical examination o		X										
Height (Screening only) and weight	X	X				X				X	X	
ECG p	X	X		X	X	X		X	X	X	X	
Heart rate and blood pressure (including orthostatic) q	X	X		X	X	X		X	X	X	X	
Respiratory rate and temperature	X	X		X	X	X		X	X	X	X	
C-SSRS r	X	X		X	X	X		X	X	X	X	
EPS (SAS, AIMS, BARS) s	X	X				X				X	X	
Prior/concomitant treatments t	←-----→											
Adverse event monitoring u		←-----→										
Laboratory												
Blood for safety laboratory sample	X	X				X				X	X	
Urine for safety laboratory	X	X				X				X	X	

Trial Periods/Phases	Screening Period a,b,c	Treatment Period										Follow-up d
		-	-	1	2	3 e	-	4	5	6 f	ET g	
Week	-2 to -1	-	-	1	2	3 e	-	4	5	6 f	ET g	10
Day	-15 to -1	1/ Baseline h	4	7±2	14±2	21±2	24	28±2	35±2	42±2	45±2	NA
Prolactin level v		X								X	X	
Serum pregnancy test w	X											
Urine pregnancy test w		X								X	X	
Urine drug screen x	X	X										
Hepatitis B, C, HIV	X											
PK blood sample			X y				X z				X aa	
Blood sample for future biospecimen research bb		X										
Other												
Daily morning dose of IMP			←-----→									

Abbreviations: AIMS=Abnormal Involuntary Movement Scale; BACS= Brief Assessment of Cognition in Schizophrenia; BARS=Barnes Akathisia Rating Scale; CGI-I=Clinical Global Impression-Improvement of Symptoms; CGI-S=Clinical Global Impression-Severity of Symptoms; C-SSRS=Columbia-Suicide Severity Rating Scale; ECG=electrocardiogram; EPS=extrapyramidal symptoms; ET=early termination; HIV=human immunodeficiency virus; IMP=investigational medicinal product; MINI=Mini International Neuropsychiatric Interview; PANSS=Positive and Negative Syndrome Scale; PK=pharmacokinetic; SAS=Simpson-Angus Scale; SF-6D=Short Form-6 Dimensions.

- a Extension of screening (up to a maximum of 21 days total) is allowed following discussion and documented approval by the medical monitor prior to the expiration of the Screening Period.
- b Subjects will be admitted to the inpatient facility at the time they sign the ICF and remain in the inpatient facility for the duration of treatment.
- c Subjects must have SARS-CoV-2 testing done with a negative test result prior to admission to the inpatient facility; refer to site procedures for additional details on testing. Additional SARS-CoV-2 testing may be performed after admission per the investigator's discretion and according to site procedures.
- d Contact with subject via phone call or other means of communication to check on their status.
- e Beginning at the Week 3 time point, subjects may receive supervised day passes for urgent issues at the investigator's discretion as described in protocol Section 4.1.2. A breathalyzer test and a urine drug screen must be performed upon return to the inpatient facility for any subject issued a supervised day pass. If the breathalyzer test is positive, the medical monitor should be contacted to determine the next steps. Subjects returning from a day pass who have a positive urine drug screen should be discontinued from the trial. However, if the positive urine drug screen results from use of marijuana (any THC containing product), prescription, or over the counter

medications or products that, in the investigator's documented opinion, does not signal a clinical condition that would impact the safety of the subject or interpretation of the trial results, the subject may continue in the trial following consultation and approval by the medical monitor.

- f A minimum of 3 days is required between the Week 6 Day 42 assessments (ie, PANSS, CGI-S, and CGI-I) and the Day 45 assessments (ie, all other scales and safety measures); eg, if the Week 6 Day 42 assessments are done on trial day 43, the earliest the Week 6 Day 45 assessments can be done is trial day 46.
- g All Week 6 (ie, both Day 42 and Day 45 time points) assessments should be completed on a single day (ie, no need for 3-day separation) for any subject who discontinues early from the trial. All assessments should be completed prior to reinitiation of antipsychotic therapy, whenever possible. If antipsychotic therapy has been initiated, the efficacy scales (PANSS, CGI-S, CGI-I) should not be conducted.
- h Unless indicated otherwise, all assessments to be completed prior to dosing.
- i Inclusion/exclusion criteria will be assessed at Baseline to ensure ongoing subject eligibility, with the exception of age or assessments that are only scheduled during Screening (eg, height for body mass index calculation). This includes the PANSS total score assessment to ensure no decrease of  $\geq 20\%$  between Screening and Baseline, as per Exclusion Criterion #4 (see protocol Section 5.2.).
- j Medical occurrences that begin before the start of dosing with IMP but after obtaining informed consent should be collected as medical and/or psychiatric history.
- k An alcohol test (breathalyzer) is required at Screening and upon return to the inpatient facility for any subject who leaves the inpatient facility. The medical monitor should be contacted to determine the next steps for subjects returning from a day pass who have a positive breathalyzer test. An alcohol test (breathalyzer) can be conducted at any time during the trial at the discretion of the investigator.
- l PANSS and CGI-S/CGI-I assessments should be completed before other assessments, following the preferred order described in protocol Section 8.
- m All responses will be relative to the subject's condition at Day 1, prior to first dose of IMP.
- n Full physical and neurological examinations should be completed at Screening and Week 6/ET. Symptom-driven physical and/or neurological examinations may be done at any time during the trial at the investigator's discretion.
- o Details for limited physical examination are provided in protocol Section 8.2.2.
- p 12-lead ECG assessments will be performed after the subject has been at rest for approximately 3 minutes. At Screening, the average of 3 consecutive ECGs collected 1 to 2 minutes apart will be used to determine subject eligibility; at Baseline, only 1 reading is required for determination of eligibility. At approximately 2 hours following dosing at weekly time points, single 12-lead ECGs will be obtained. Additional ECGs can be performed at the investigator's discretion (eg, if abnormalities are noted).
- q At Screening and Baseline, blood pressure and heart rate assessments should be performed in order to confirm eligibility (see Exclusion Criterion in protocol Section 5.2). Triplicate supine heart rate and blood pressure measurements should be taken at approximately 1-minute intervals predose (Day 1 only, Baseline), and at approximately 2 hours after dosing on Day 1 and Weeks 1 through 6. The triplicate supine heart rate and blood pressure measurements will be followed by a single measurement after approximately 2 minutes in a standing position to allow for orthostatic assessments. Additional time points can be added at the investigator's discretion (eg, if abnormalities are noted).
- r The "Baseline/Screening" C-SSRS form will be completed for all subjects at Screening to determine eligibility and the "Since Last Visit" C-SSRS form will be completed at Baseline to ensure that the subject continues to qualify for the trial. The "Since Last Visit" C-SSRS form will also be completed at weekly time points after Baseline.
- s EPS assessments can be completed at any time during the trial, per investigator discretion, if symptoms are present.
- t Prior and concomitant medications should be recorded from Screening through the subject's last visit/contact.
- u Adverse events (serious and nonserious) should be recorded from the first dose of IMP through the subject's last visit/contact.
- v The Week 6 prolactin results will be partially blinded; the investigator will be notified if the prolactin levels exceed a predefined limit with instructions to send the subject for appropriate follow-up.

- w For women of childbearing potential only. Pregnancy tests can be performed at any time during the trial at the discretion of the investigator if pregnancy is suspected. Any urine pregnancy tests that are positive must be confirmed using a serum test.
- x A urine drug screen is required at Screening (full panel including opioids) and Baseline (dipstick); see the exclusion criteria for exclusions based on the urine drug screen. In addition, the urine drug screen will be conducted upon return to the inpatient facility for any subject who leaves the inpatient facility as described in protocol Section 4.1.2. Subjects returning from a day pass who have a positive urine drug screen will be discontinued from the trial. The urine drug screen can be conducted at any time during the trial at the discretion of the investigator.
- y PK samples (1 sample and 1 backup sample) will be taken predose (within 15 minutes prior to dosing) and at 1, 4, and 8 hours following dosing on Day 4.
- z PK samples (1 sample and 1 backup sample) will be obtained predose (within 15 minutes prior to dosing) and at 1, 2, 4, 8, 12, and 24 hours following administration of emraclidine on Day 24.

aa A single PK sample will be collected from subjects at time of discontinuation; the actual date and time of sample collection will be documented.

bb Future biospecimen research sample is optional and is only to be collected if signed consent is obtained from the subject. Sample can be collected at any time following confirmation of subject eligibility and prior to initiation of first dose.

## 9.2. Columbia-Suicide Severity Rating Scale (C-SSRS) Suicidal Ideation and Suicidal Behavior Scores

The C-SSRS is comprised of 10 categories with binary responses. The 10 categories include:

Category 1 – Wish to be Dead

Category 2 – Non-specific Active Suicidal Thoughts

Category 3 – Active Suicidal Ideation with Any Methods (Not Plan) without Intent to Act

Category 4 – Active Suicidal Ideation with Some Intent to Act, without Specific Plan

Category 5 – Active Suicidal Ideation with Specific Plan and Intent

Category 6 – Preparatory Acts or Behavior

Category 7 – Aborted Attempt

Category 8 – Interrupted Attempt

Category 9 – Actual Attempt (non-fatal)

Category 10 – Completed Suicide

Categories 1-5 represent Suicidal Ideation and categories 6-10 represent Suicidal Behavior. Each category is scored as 1 if there is a positive response in the category and a 0 if there are no positive responses in the category.

### Self-Injurious Behavior Without Suicidal Intent During Treatment

A subject will be categorized as having self-injurious behavior without suicidal intent if there is an occurrence of non-suicidal self-injurious behavior at any post-baseline visit.

### Baseline C-SSRS Score

Baseline represents the pre-treatment assessment of recent history, with elements of suicidal ideation assessed over the prior 6 months and elements of suicidal behavior assessed over the prior 2 years. It is scaled from 0 (no suicidal ideation or behavior) to 10 (completed suicide).

### Treatment-Emergent Suicide-Related Event

A subject will be categorized as having a treatment-emergent suicide-related event if at least one post-baseline suicidal ideation or suicidal behavior score is greater than 0.

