9.	
Diagnosis of moderate to severe substance or alcohol-use disorder (excluding nicotine or caffeine) as per DSM-5 criteria within 12 months prior to signing the ICF.
 
Participants with mild substance or alcohol-use disorder may be included in the trial following consultation and approval by the medical monitor.

10.	
“Yes” responses for any of the following items on the C-SSRS (within the past 6 months):
 
 • Suicidal Ideation Item 4 (Active Suicidal Ideation with Some Intent to Act, without Specific Plan) • Suicidal Ideation Item 5 (Active Suicidal Ideation with Specific Plan and Intent) 
“Yes” responses for any of the following items on the C-SSRS (within past 2 years):
 
 • Any of the Suicidal Behavior items (Actual Attempt, Interrupted Attempt, Aborted Attempt, Preparatory Acts or Behavior) 
Serious risk of suicide in the opinion of the investigator is also exclusionary.

11.	
Any condition or surgery that could possibly affect drug absorption, including, but not limited to, complicated appendectomy or cholecystectomy, bowel resections, bariatric weight loss surgery, gastric banding, or gastrectomy.

12.	
Have recently been diagnosed with and hospitalized for symptomatic COVID-19 or test positive for SARS-CoV-2 at Screening.

Prior or Concomitant Therapies	
13.	
Use of prohibited medications prior to randomization within the required wash-out period (Table 4) or likely to require prohibited concomitant therapy (Table 5) during the trial.

14.	
Transcranial magnetic stimulation or electroconvulsive therapy within 90 days of signing the ICF.

Laboratory Test Results	
15.	
Positive result for HIV antibody, hepatitis B surface antigen, or hepatitis C antibody with detectable viral RNA levels at Screening.
 
Note: Positive or indeterminate test result for hepatitis C antibody should follow with hepatitis C virus PCR RNA test. If result is positive, the participant is excluded.

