#### **5.15.7. Columbia-Suicide Severity Rating Scale (C-SSRS)**

The maximum post-baseline results from the C-SSRS will be summarized. The maximum of each subscale (suicidal ideation [Categories 1-5], suicidal behavior [Categories 6-10], suicidal ideation or behavior [Categories 1-10], and self-injurious behavior without suicidal intent) will be presented. The number of patients with suicide-related treatment-emergent events, treatment-emergent suicidal ideation, and suicidal behavior, based on a comparison of the C-SSRS at baseline and/or previous lifetime experience to maximum C-SSRS scores across all post-baseline assessments will be provided for each treatment. All C-SSRS elements will be reflected in a listing.

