### Treatment-Emergent Suicidal Ideation Compared to Recent History

A subject will be categorized as having treatment-emergent suicidal ideation compared to recent history when there is at least one post-baseline suicidal ideation score  $> 0$  and is an increase from baseline. Subjects with missing ideation in recent history and at least one post-baseline suicidal ideation score  $> 0$  will be categorized as having treatment-emergent suicidal ideation. Lifetime scores are not considered for baseline suicidal ideation responses.

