### Treatment-Emergent Serious Suicidal Ideation Compared to Recent History

A subject will be categorized as having treatment-emergent serious suicidal ideation compared to recent history if the baseline score was  $< 4$  and the post-baseline suicidal ideation score increases

to 4 or 5. Subjects with missing ideation in recent history and at least one post-baseline suicidal ideation score of 4 or 5 will be categorized as having treatment-emergent serious suicidal ideation. Lifetime scores are not considered for baseline suicidal ideation responses.

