#### Emergence of Suicidal Behavior Compared to all Prior History

A subject will be categorized as having emergence of suicidal behavior compared to all prior history if there had been no suicidal behavior in Categories 6-10 reported at any pre-treatment assessment, including responses to lifetime history questions, and there is at least one positive post-baseline C-SSRS assessment in Categories 6-10. Subjects with missing suicidal behavior at any pre-treatment assessment, and there is at least one post-baseline suicidal behavior score will be categorized as having emergence of suicidal behavior. ‘All Prior History’ represents lifetime history.

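### SAP 9.2 counts any post-baseline C-SSRS score above 0 as a treatment-emergent suicide-related event, while SAP 5.15.7 bases that count on a comparison with baseline or lifetime history

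*SAP*

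**What the plan says.** SAP 3.2.6 sends the reader to Section 9.2 for the definition of treatment-emergent C-SSRS events. There, under *Treatment-Emergent Suicide-Related Event*, a participant qualifies "if at least one post-baseline suicidal ideation or suicidal behavior score is greater than 0". Nothing else is required.

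SAP 5.15.7 names the outputs as "suicide-related treatment-emergent events, treatment-emergent suicidal ideation, and suicidal behavior" and says that the numbers are "based on a comparison of the C-SSRS at baseline and/or previous lifetime experience to maximum C-SSRS scores across all post-baseline assessments".

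The other emergence categories in 9.2 each look back:

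- Treatment-emergent ideation needs a positive post-baseline score "and is an increase from baseline".
- Treatment-emergent serious ideation needs a baseline below 4, and applies when "the post-baseline suicidal ideation score increases" to 4 or 5.
- Emergence of serious ideation needs a baseline of 0.
- Emergence of suicidal behavior applies "if there had been no suicidal behavior in Categories 6-10 reported at any pre-treatment assessment", lifetime history included.

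The baseline score needed for such a comparison is already defined in 9.2, with "elements of suicidal ideation assessed over the prior 6 months and elements of suicidal behavior assessed over the prior 2 years".

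On eligibility, Exclusion Criterion 10 in Protocol 5.2 lists "Suicidal Ideation Item 4 (Active Suicidal Ideation with Some Intent to Act, without Specific Plan" and item 5 (both within 6 months), and any suicidal behavior item within 2 years. It also excludes anyone the investigator considers at serious risk of suicide. Ideation items 1 to 3 are not listed.

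**The concern.** Two sections of the SAP give different rules for one row. Under 5.15.7 the row should show what is new or worse relative to history. Under 9.2 it shows anyone with a positive score after baseline. A participant who enters with ideation category 3 and improves to category 1 is then a treatment-emergent suicide-related event, although the ideation definition that follows in 9.2 says the same participant does not have treatment-emergent ideation.

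Suicidality on the C-SSRS is a named safety endpoint under the secondary objective (Protocol Section 3, SAP Section 2). At stake are the absolute rate printed under the treatment-emergent label and the clarity of any contrast between arms. There is also a practical risk: SAP 9.4 requires verification by independent programming, and a programmer working from 5.15.7 and one working from 9.2 could produce different counts.

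**Working it through.** The plan states no C-SSRS rate or sample size, so there is no figure of its own to reproduce. The check is an enumeration of scores followed by an illustration with assumed rates.

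**1. Which score pairs are affected.** Inputs: baseline ideation 0 to 3 (items 4 and 5 excluded by Protocol 5.2), maximum post-baseline ideation 0 to 5 (SAP 9.2), no suicidal behavior. That gives 4 × 6 = 24 pairs. Rule A is the 9.2 event definition: post > 0. Rule B adds the condition used for treatment-emergent ideation: post > 0 and post > baseline.

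| Baseline | Flagged by A | Flagged by B | Flagged by A only (post score) |
|---|---|---|---|
| 0 | 5 | 5 | none |
| 1 | 5 | 4 | 1 |
| 2 | 5 | 3 | 1, 2 |
| 3 | 5 | 2 | 1, 2, 3 |
| Total | 20 | 14 | 6 |

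Of the six pairs flagged by A only, three are unchanged, (1,1), (2,2) and (3,3), and three are improved, (2,1), (3,1) and (3,2). The fraction 6 of 24 counts score combinations. It is not an estimate of how many participants are affected.

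**2. Why behavior adds little.** Suicidal behavior in the 2 years before entry is excluded, and post-baseline scores come from the Since Last Visit form. Older behavior does not by itself score after baseline, so the discrepancy is essentially confined to baseline ideation of 1 to 3.

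**3. Possible size.** The arm size of 124 is from Protocol 4.1.2. The rates are assumptions: 2% of participants truly new or worsened, and a share *s* with baseline ideation of 1 to 3 that persists at the same or a lower positive score.

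- Baseline-referenced count: 124 × 0.02 = 2.5 per arm.
- Count under the 9.2 rule: 124 × (0.02 + *s*).
  - *s* = 2%: 124 × 0.04 = 5.0
  - *s* = 5%: 124 × 0.07 = 8.7
  - *s* = 10%: 124 × 0.12 = 14.9

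The ratio to the baseline-referenced count runs from 0.04/0.02 = 2 to 0.12/0.02 = 6, and depends entirely on the assumed rates.

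**4. Overlap with another output.** SAP 5.15.7 already summarizes the maximum post-baseline result over Categories 1 to 10. A maximum above 0 identifies the same participants as the 9.2 event rule, so the row as written repeats that count under a different label.

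**The case against.** The best defense is that the 9.2 row is a deliberately inclusive on-treatment count. Its heading lacks the comparison phrase that the later categories carry, the rule can be programmed as it stands, and the general TEAE definition in SAP 3.2.1.2 also works by timing. It might be added that the comparison phrase in 5.15.7 attaches only to the last item of its list. The first part has force: an inclusive row is a legitimate safety display. It does not settle the matter, because 5.15.7 places the comparison after the whole list, and because the label still asserts emergence under a rule that ignores baseline.

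A second argument is that an unchanged score is not always unchanged ideation. Baseline covers 6 months and the post-baseline form covers the time since the last visit. A participant with category 1 ideation months before entry, none at Day 1 and category 1 again at Week 3 has a recurrence on treatment. This stands. It is a reason not to replace the row with one that only requires an increase.

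Third, eligibility is narrower than the listed items suggest. Investigator-judged serious suicide risk is exclusionary, and Exclusion Criterion 1 removes major depressive disorder and recent acute depressive symptoms that need an antidepressant. This also stands, but neither provision bars items 1 to 3 as such.

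Fourth, baseline-referenced ideation, serious ideation and behavior are reported separately, all C-SSRS elements are listed, and no hypothesis test uses the row. This stands and limits the consequence. It does not correct the label on the composite row.

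**Conclusion.** The inconsistency is real. The operative definition in 9.2 has no baseline condition, 5.15.7 says there is a comparison, and no other section supplies one. Participants with baseline ideation of 1 to 3 who are unchanged or improved but still positive would be reported as treatment-emergent.

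The consequence is limited to a descriptive safety row that sits beside correctly defined rows. Efficacy inference and type I error are untouched.

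Three stronger conclusions might be inferred, and the documents support none of them:

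- *That pre-existing ideation would dominate the row, or inflate it by a known multiple.* No baseline ideation rate is given. The rise from about 2.5 to about 5 to 15 per arm rests on the assumed rates.
- *That the row is biased for or against emraclidine.* Randomization should balance baseline ideation on average, so over-counting is expected in all arms. An equal addition to each arm leaves the difference unchanged in expectation and pulls the ratio toward 1. Persistence could differ by treatment, but nothing in the documents indicates a direction.
- *That every extra case is a false event.* Some would be genuine recurrences on treatment.

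**What to change.** Rename the 9.2 row *any post-baseline suicidal ideation or behavior*. Amend 5.15.7 so that it lists this row as a simple post-baseline count, and keep the term treatment-emergent for the rows that refer to baseline or prior history.

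If a treatment-emergent composite is also wanted, define it as a maximum post-baseline C-SSRS category (0 to 10) that is above 0 and above the baseline category. Carry over the missing-baseline rule from the treatment-emergent ideation definition, under which missing recent history with a positive post-baseline score counts as emergent. Keep the any-post-baseline row beside it so that on-treatment recurrences stay visible.

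The cost is a sentence or two in 9.2, a matching edit in 5.15.7 and a table label, with one extra row if the composite is kept. No new data are needed. The change should be made before unblinding.
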